 12.1. Appendix I: Imputation of Missing Dates40

1. Version History

Version	Summary of Changes	Author(s)/Title
1.0	
 First draft 	[name], Senior Principal Statistician
2.0	
 Study populations updated. ABPM algorithm updated. Subgroup analyses updated 	[name], Senior Principal Statistician
3.0	
 Updated to new template. Study populations updated 	[name], Senior Principal Statistician
4.0	
 Powered SPYRAL HTN-ON MED Study 	[name], Senior Principal Statistician
4.1	
 Bayesian design updated to remove test for expected success Changes to discount function formulation 	[name], Senior Principal Statistician
4.2	
 Per-protocol population updated to exclude subjects who did not receive their randomized treatment Treatment effect for efficacy analysis updated so that a negative direction favors RDN Stochastic comparison in section 9.9.4.1 updated Prior distribution and hyper-parameter definitions in section 9.9.4.1 updated Section 9.4 updated to include an analysis to impute missing outcome data Subgroup analyses in section 9.11 updated Appendices II, III and IV updated to include unscheduled visits corresponding to repeat ABPM visits 	[name], Senior Principal Statistician
4.3	
 Updated language to reflect "approximately 149" subjects included in the first interim analysis due to variable attrition rate 	[name], Senior Principal Statistician
4.4	
 Updated hyperparameter value for b_{β} to be $1e10$, changed from $1e5$ 	[name], Senior Principal Statistician
5.0	
 First and second interim analysis to take place with 95 and 149 randomized subjects. Sections 8, 9.8, 9.9.4.3, 9.9.5 updated. 	[name], Senior Principal Statistician

	
 • Section 9.12 added describing analyses related to COVID-19 • As Treated population added in 9.1.3.4 • Added “y_i is the BP change for the ith observation and x_i is the mean centered baseline BP for the ith observation” to section 9.9.4.1. for the definition of the x_i and y_i model parameters • Added “mean centered” to section 9.9.4.1. COMBINE for the definition of the x_i model parameter • Updated Table 3 in section 9.9.4.3 to include 2 decimal places for prior treatment effects • Interim analysis stopping rules in section 9.8 clarified to state that enrollment will stop if stopping rules are met • Primary safety analysis section 9.9.1.1. updated to clarify that primary safety analysis will only be performed once using first 253 subjects • Primary Efficacy Endpoint Analysis section 9.9.4 updated to indicate that the primary analysis treatment effect is Bayesian posterior estimate • Section 9.9.5 updated to include frequentist ANCOVA analyses as secondary analysis of primary efficacy endpoints. Also specifies that secondary cohort subjects will be analyzed using frequentist ANCOVA and will be performed internally • Added attrition rate of 15% to Table 3 in section 9.9.4.3 • Subgroup analyses section updated to include same as OFFMED, to specify complements for every subgroup, and to indicate which subgroups analyses are restricted to the RDN arm • Appendix I (missing data imputation) updated • Appendix VII (section 11.7) added with sensitivity analyses of Bayesian operating characteristics 	

5.1
	
 • First and second interim analysis to take place with 130 and 175 randomized subjects. Sections 8, 9.8, 9.9.4.3, 9.9.5 updated • Bayesian sensitivity analyses added in section 9.9.5 • Appendices describing the algorithms for selecting office BP, 24-hour BP, lab values 	
[name], Senior Principal Statistician

	
and drug testing values removed from SAP, and will only be included in study table specifications
 
 • Validation requirements added in section 10. • SAP template version added to footer 	
5.2	
 • Subgroup analyses for accessory arteries treated and 1 vs. 2 vs. 3 AH Medication Classes at baseline added in section 9.11 	[name], Senior Principal Statistician
5.3	
 • Win ratio analyses and reference added to section 9.9.9 • HTN Burden analyses and reference added to section 9.9.10 • % Time in Target Range (TTR) analyses and reference added in section 9.9.11 	[name], Senior Principal Statistician
5.4	
 • Three new Medication Adherence analysis populations added to section 9.1.3 • Witnessed pill intake and BP protocol deviations added to Additional Objectives in section 9.9.8 	[name], Senior Principal Statistician
5.5	
 • Win Ratio section 9.9.9 updated • TTR section 9.9.10 updated • HTN Burden section removed 	[name], Senior Principal Statistician

2. List of Abbreviations and Definitions of Terms

Abbreviation	Definition
ABPM	Ambulatory Blood Pressure Monitoring
AE	Adverse Event
ANCOVA	Analysis of Covariance
BP	Blood Pressure
CIP	Clinical Investigation Plan
DBP	Diastolic Blood Pressure
DSMB	Data Safety Monitoring Board
eGFR	estimated Glomerular Filtration Rate
ESRD	End Stage Renal Disease
MAE	Major Adverse Events
MCMC	Markov Chain Monte Carlo
OBP	Office Blood Pressure
SAP	Statistical Analysis Plan
SBP	Systolic Blood Pressure
SV2	Screening Visit 2

3. Introduction

This document outlines the detailed statistical methods to be implemented for the data collected within the scope of the Medtronic Vascular SPYRAL HTN-ON MED Study: Global Clinical Study of Renal Denervation with the Symplicity Spyral™ Multi-Electrode Renal Denervation System in Patients with Uncontrolled Hypertension on standard medical therapy. The purpose of this study is to test the hypothesis that renal denervation decreases blood pressure and is safe when studied in the presence of up to three standard antihypertensive medications. Specifically, the SAP has the following purpose: to prospectively outline the types of analyses and presentations of data that will form the basis for conclusions to be reached that will answer the trial objectives outlined in the protocol, and to explain in detail how the data will be handled and analyzed, adhering to commonly accepted standards and

practices of biostatistical analysis in the medical device industry. Results obtained from the analyses outlined in this document will be the basis of the Clinical Study Report for this trial.

4. Study Objectives

The objective of this study is to test the hypothesis that renal denervation is safe and reduces systolic blood pressure (SBP) in patients with uncontrolled hypertension on one, two, or three standard antihypertensive medications compared to a sham-controlled population. In this study, "uncontrolled hypertension" is defined as an office systolic blood pressure (SBP) ≥ 150 mmHg and < 180 mmHg, an office Diastolic Blood Pressure (DBP) ≥ 90 mmHg and a 24-hour Ambulatory Blood Pressure Monitoring (ABPM) average SBP ≥ 140 mmHg to < 170 mmHg, all of which are measured at screening visit 2. Data obtained will be used to confirm the effect of renal denervation on elevated blood pressure in patients on 1, 2 or 3 anti-hypertensive medications. Data collected during the SPYRAL HTN-ON MED trial may be used to gain market approval or additional indications for the Symplicity Spyral™ multi-electrode renal denervation catheter (Symplicity Spyral™ catheter) and the Symplicity G3™ renal denervation RF generator from regulatory entities, including, but not limited to: the Pharmaceuticals and Medical Device Agency (PMDA), Health Canada, and the U.S. Food and Drug Administration (FDA).

5. Study Endpoints

5.1. Primary Endpoints

There are two primary endpoints in this study (one efficacy and one safety). The study will be considered successful if both the primary safety and efficacy endpoint hypotheses are met.

Powered Primary Efficacy Endpoint:

Baseline adjusted change (using analysis of covariance, ANCOVA) in SBP from baseline (screening visit 2, SV2) to 6 months post-procedure as measured by 24-hour ABPM.

Powered Primary Safety Endpoint:

Incidence of Major Adverse Events (MAE), defined as a composite of the following events, through one-month post-randomization (6 months for new renal artery stenosis):

- All-cause mortality
- End-Stage Renal Disease (ESRD)
- Significant embolic event resulting in end-organ damage
- Renal artery perforation requiring intervention
- Renal artery dissection requiring intervention
- Vascular complications
- Hospitalization for hypertensive crisis not related to confirmed non-adherence with medications and/or the protocol
- New renal artery stenosis $> 70\%$, confirmed by angiography and as determined by the angiographic core laboratory

5.2. Secondary Endpoints

Secondary Efficacy Endpoints

- Change in SBP from baseline (screening visit 2) as measured by 24-hour ABPM at 3, 6, 12, 24 and 36 months post-procedure
- Change in office systolic blood pressure from baseline (screening visit 2) at 1, 3, 6, 12, 24 and 36 months post-procedure
- Change in diastolic blood pressure from baseline (screening visit 2) as measured by 24-hour ABPM at 3, 6, 12, 24 and 36 months post-procedure
- Change in office diastolic blood pressure from baseline (screening visit 2) at 1, 3, 6, 12, 24 and 36 months post-procedure
- Incidence of achieving target office systolic blood pressure (SBP <140 mmHg) at 1, 3, 6, 12, 24 and 36 months post-procedure

Secondary Safety Endpoints

Acute/procedural safety at 1-month post-procedure

- Significant embolic event resulting in end-organ damage
- Renal artery perforation requiring intervention
- Renal artery dissection requiring intervention
- Vascular complications
- End-stage renal disease
- $\geq 40\%$ decline in eGFR
- Increase in serum creatinine $> 50\%$ from screening visit 2
- New myocardial infarction
- New stroke
- Renal artery re-intervention
- Major bleeding according to TIMI definition (i.e. intracranial hemorrhage, $\geq 5\text{g/dl}$ decrease in hemoglobin concentration, a $\geq 15\%$ absolute decrease in hematocrit, or death due to bleeding within 7 days of the procedure)
- New renal artery stenosis $> 70\%$, confirmed by angiography and as determined by the angiographic core laboratory
- Hospitalization for hypertensive crisis not related to confirmed non-adherence with medication and/or protocol

Chronic Safety Secondary Endpoints at 3, 6, 12, 24 and 36 months post-procedure

- Composite Safety Endpoint, defined as a composite of the following events:
 - All-cause mortality
 - End-stage renal disease (ESRD)
 - Significant embolic event resulting in end-organ damage
 - Renal artery perforation requiring intervention
 - Renal artery dissection requiring intervention
 - Vascular complications
 - Hospitalization for hypertensive crisis not related to confirmed non-adherence with medications and/or the protocol
 - New renal artery stenosis $> 70\%$, confirmed by angiography and as determined by the angiographic core laboratory

- $\geq 40\%$ decline in eGFR
- Increase in serum creatinine $> 50\%$ from screening visit 2
- New myocardial infarction
- New stroke
- Renal artery re-intervention
- Major bleeding according to TIMI definition (i.e. intracranial hemorrhage, $\geq 5\text{g/dl}$ decrease in hemoglobin concentration, a $\geq 15\%$ absolute decrease in hematocrit, or death due to bleeding within 7 days of the procedure)
- Hospitalization for hypertensive crisis not related to confirmed non-adherence with medication and/or protocol

Summary of Health-related Quality of Life (HRQoL) analysis based on reporting measures using accepted QoL instruments (EQ5D)

Additional analyses

The following additional analyses will be conducted:

- Antihypertensive medication usage throughout the study, including escape patients and subjects with medication changes within 6-month follow-up.
- Additional procedural characteristics e.g. treatment duration, frequency of distal renal artery treatment, ablations per vessel, location of ablations, number of ablations per patient and other characteristics will be analyzed to assess their impact on blood pressure.
- Medication adherence will be assessed using results from drug testing. In addition, we will perform analyses to evaluate the effect of medications adherence on BP.
- Analyses looking at long term imaging will be performed.

6. Investigation Plan

The SPYRAL HTN-ON MED study is a multi-center, international, prospective, blinded, randomized, interventional, sham-controlled study. The goal is to demonstrate that catheter-based renal denervation using the Symplicity Spyral catheter and the Symplicity G3 generator is an effective and safe treatment for hypertension when studied in the presence of one, two, or three anti-hypertensive medication classes. Subjects must be on at least 50% of the maximum manufacturer's dosage of antihypertensive medication. Anti-hypertensive medication classes must include a thiazide-type diuretic, a dihydropyridine calcium channel blocker, an ACE-I/ARB, or a beta blocker, (when prescribed with other qualifying medications, 12.5 mg hydrochlorothiazide is acceptable as the minimum dosage).

7. Randomization and Blinding

Randomization will be stratified by study center at a 2:1 (RDN to control) ratio to:

- Denervation group (RDN): Subjects remain blinded and are treated with the renal denervation procedure.
- Control group: Subjects remain blinded and remain on the catheterization lab table for at least 20 minutes prior to introducer sheath removal.

Investigational sites will access randomization allocation via a password-protected system that can only be accessed by those approved by the study sponsor.

All study staff and necessary hospital personnel will be instructed that subjects are not to be informed of their randomization assignments and appropriate measures should be taken to minimize the risk of premature unblinding.

The Investigator performing the catheterization lab procedures and his/her designated study staff will be blinded to a subject's randomization group up until the angiography is completed and inclusion/exclusion confirmed following the angiography. However, investigators performing study follow-up visits and the subject's referring/managing physicians will not be proactively informed of a subject's treatment assignment to minimize potential bias in the subject's care decisions. To minimize potential bias in the measurement of Office BP and ABPM, each investigational site will specify several designated "blinded" members of their study staff that will not be informed of the subject's group assignments and will be responsible for performing the office blood pressure measurements, conducting ABPM preparation and printing results upon a patient completing the ABPM. Prior to unblinding, the effectiveness of blinding will be assessed by asking blinded study staff which group they believe the subject was randomized to.

Subjects will be blinded during the renal angiogram by a combination of conscious sedation, sensory isolation (e.g., blindfold and music), and lack of familiarity with the procedural details and duration (i.e., subjects will not know the difference between the renal angiography procedure alone and the renal angiography and denervation procedure). Subjects will continue to be blinded by only interacting with blinded site personnel through the 6-month follow-up visit post-procedure. Blinding effectiveness will be assessed by asking the subject which group they believe they were randomized to. All subjects will be unblinded after the completion of their required 6-Month follow-up testing.

8. Determination of Sample Size

This study will be conducted as an adaptive Bayesian trial with an informative prior. A Bayesian power prior approach [3,4] in conjunction with a discount function will be used to incorporate the prior data. The discount function reduces the strength of the prior data if disagreements are observed with the prospective data.

The prior data consists of the first consecutively randomized 80 subjects in the SPYRAL HTN-ON MED study, which were randomized in a 1:1 ratio to RDN or control. The results from these 80 subjects have already been analyzed and published [6].

The prospective data consists of the following two cohorts:

[figure not shown]
1. Subjects 81 to 106 which have already been enrolled and were randomized in a 1:1 ratio to RDN vs. control, and whose data has not been unblinded and analyzed by Medtronic.
2. All remaining subjects in the SPYRAL HTN-ON MED Study from 107 onwards which will be randomized in a 2:1 ratio to RDN vs control.

The weight of the prior data will be adjusted using a discount function, which scales from 0 to 1, according to the similarity of the prior and prospective data. The discount function adjusts the amount of weight the prior receives. This prevents the use of an informative prior where exchangeability issues are present (e.g., the prior and prospective data are quite different). This discount function approach was proposed by the Medical Device Innovative Consortium (MDIC) working group and is a collaborative

effort between FDA and industry through the MDIC [1,2]. If the analyses show a high level of agreement for prospective data compared to the prior, the prior will be weighted at or near 100%. If the prospective data perform much worse than or much better than the prior, then the prior will receive very little or zero weight. The Bayesian adaptive design is set up to enroll patients until a sufficient sample size is achieved to have high probability of meeting the endpoint.

The sample size of the study will vary from a minimum of 110 to 221 subjects with evaluable data due to the adaptive nature of the trial. This will require approximately 130 to 260 randomized subjects assuming a 15% rate of attrition at 6-months.

- The first interim analysis will take place when we have a minimum of 110 subjects with evaluable data. With an expected attrition rate of 15%, this will require approximately 130 randomized subjects. If the attrition rate is higher than 15%, then additional subjects will be randomized in order to reach a minimum of 110 evaluable subjects.
- The second interim analysis will take place when we have a minimum of 149 subjects with evaluable data. With an expected attrition rate of 15%, this will require 175 randomized subjects. If the attrition rate is higher than 15%, then additional subjects will be randomized in order to reach a minimum of 149 evaluable subjects.
- If the study does not stop at the first or second interim analyses, then the final look will take place when 260 subjects have been randomized. This will result in 221 evaluable subjects based on a 15% attrition rate.

Simulations of trial design operating characteristics performed to demonstrate control of type I error and power are presented in section 9.9.4.3 for the primary efficacy endpoint.

9. Statistical Methods

9.1. Study Subjects

9.1.1. Disposition of Subjects

A subject disposition table will be provided for each follow-up visit containing the following information:

- The number of subjects who died or withdrew prior to each follow-up
- The number of subjects eligible for each follow-up visit
- The number of subjects completing each follow-up visit within the protocol specified window
- The number of subjects completing each follow-up outside the protocol specified window
- The number of subjects who did not complete their follow-up

9.1.2. Clinical Investigation Plan (CIP) Deviations

A study deviation is an event where the investigator or investigational site personnel did not conduct the clinical study according to the Clinical Investigation Plan or Clinical Study Agreement. The investigator is not allowed to deviate from the above mentioned documents except with prior approval and under emergency circumstances. All deviations shall be documented and explained, regardless the reason for the deviation. Medtronic will assess the significance of all deviations and evaluate the need to amend the Clinical Investigation Plan or to early terminate the investigation, in accordance with Medtronic SOPs.

9.1.3. Analysis Sets

9.1.3.1. Intention-To-Treat (ITT) Population

All randomized subjects analyzed according to their randomized treatment. Subjects who meet the anti-hypertensive medication escape criteria (office SBP ≥ 180 mmHg or < 115 mmHg associated with symptoms of hypotension or safety concern requiring medication changes) will be analyzed using Last Observation Carried Forward (LOCF) for their blood pressure measurements. Safety outcomes, and office and ambulatory blood pressure outcomes at each follow-up visit will be presented for this population.

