9.9.6. Secondary Analysis of Primary Efficacy Endpoint

As a secondary analysis of the powered primary efficacy endpoints, frequentist ANCOVA methods will be used to determine the baseline adjusted treatment effect for the study populations defined in section 9.1.3.

As outlined in section 9.8, the first and second interim analyses takes place when a minimum of 110 and 149 subjects have 6-month follow-up ABPM data available respectively. At each interim analysis, the Bayesian efficacy analysis will be performed and, if the pre-specified stopping rules are met, then enrollment will be stopped. If the study stops for efficacy or futility at either the first or second interim analysis, then any additional subjects that have been enrolled before the decision to stop has been made will not be part of the primary endpoint analysis, but instead will be pooled with the existing subjects and analyzed as a secondary cohort. This analysis will be performed using frequentist ANCOVA methods to determine the baseline adjusted treatment effect and will be performed by Medtronic, as Medtronic will be unblinded at this stage.

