9.9.7. Secondary Efficacy Objectives

The following additional secondary efficacy endpoints will be assessed:

- Change in SBP from baseline (SV2) as measured by 24-hour ABPM at 3, 6, 12, 24 and 36 months post-procedure.
- Change in office SBP from baseline (SV2) at 1, 3, 6, 12, 24 and 36 months post-procedure.
- Change in DBP from baseline (SV2) as measured by 24-hour ABPM at 3, 6, 12, 24 and 36 months post-procedure.
- Change in office DBP from baseline (SV2) at 1, 3, 6, 12, 24 and 36 months post-procedure.

- Incidence of achieving target office SBP (SBP <140 mmHg) at 1, 3, 6, 12, 24 and 36 months post-procedure.

RDN vs. control groups will be compared out to 6-months post randomization, prior to the crossover procedure. Statistical comparisons will be performed using the independent samples t-test for continuous endpoints and Fisher's exact test for categorical endpoints. In addition, two-sided 95% confidence intervals of the difference between RDN and control groups will be presented. Changes in blood pressure measurements from baseline to follow-up within each treatment group will be assessed using paired t-tests. Two-sided 95% confidence intervals of the mean change from baseline will be presented for each treatment group. analysis of covariance (ANCOVA) models, adjusting the treatment effect for the baseline BP measurements will also be applied to all continuous secondary endpoints.

RDN vs. crossover vs. non-crossover groups will be compared out to 36 months post-procedure using chi-square tests for categorical data and ANOVA for continuous data.

Changes in blood pressure measurements from baseline to follow-up within each group will be assessed using paired t-tests. Two-sided 95% confidence intervals of the mean change from baseline will also be presented for each group.

The secondary efficacy analyses will be presented for all the study populations defined in section 9.1.3.

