The ITT population, including the full feasibility cohort, will be used. For medication INDEX2, drug testing data will be used at SV2 and 6-months if available, otherwise the medication burden will be determined using prescribed medication data.

Two additional win ratio sensitivity analyses will be performed using thresholds of 3.5 and 0 mmHg for the 24Hr SBP endpoint and keeping the threshold of zero for the medication burden endpoint. The R package BuyseTest version 2.2.6 will be used to perform these analyses.

9.9.10. % Time in Target Range (TTR%) Analyses

Time in target range (TTR%) analyses [16], which calculate the percentage of time that a subject's BP is within pre-specified BP ranges will be calculated by performing linear interpolation over the days between successive BP measurements, including data from both the baseline and follow-up periods, and summarizing over the entire follow-up time period. Subjects must have a minimum of 2 BP measurements within the TTR time interval to be included in the calculation. All follow-up visits will be included in the TTR analyses. Office SBP TTR will be evaluated using a range of ≤ 140 mmHg and 24Hr SBP TTR will be evaluated using ranges of ≤ 140 & ≤ 130 mmHg. In addition, we will combine Office TTR (≤ 140 mmHg) with 24Hr SBP TTR (≤ 130 mmHg) by taking the maximum value for each subject within the TTR time interval.

For each subject we will calculate their TTR%, using the BP endpoints and BP ranges specified above, in the following time intervals:

- TTR% from baseline to 6-months
- TTR% from baseline to 12-months
- TTR% from baseline to 24-months

- TTR% from baseline to 36-months

These results will be tabulated and compared between treatment arms using non-parametric Kruskal-Wallis tests.

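### The frequentist and secondary efficacy analyses do not fix whether the 80 already published subjects are included; read literally they are, at full weight, and the win ratio includes them explicitly

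*SAP*

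**What the plan says.** Section 8 splits one randomised study into prior and prospective data. On the prior it says: "The prior data consists of the first consecutively randomized 80 subjects in the SPYRAL HTN-ON MED study", and "The results from these 80 subjects have already been analyzed and published". The prospective data are "Subjects 81 to 106 which have already been enrolled and were randomized in a 1:1 ratio to RDN vs. control", followed by those "from 107 onwards which will be randomized in a 2:1 ratio to RDN vs control".

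Section 9.1.3.1 defines ITT as "All randomized subjects analyzed according to their randomized treatment". The modified ITT, per-protocol, three medication-adherence and as-treated sets also start from all randomised subjects. None refers to the split in section 8.

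Three efficacy sections then rely on these sets:
- Section 9.9.6: "frequentist ANCOVA methods will be used to determine the baseline adjusted treatment effect for the study populations defined in section 9.1.3".
- Section 9.9.7: "The secondary efficacy analyses will be presented for all the study populations defined in section 9.1.3".
- Section 9.9.9, which calls the 6-month win ratio a prospective secondary analysis: "The ITT population, including the full feasibility cohort, will be used".

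The primary Bayesian analysis (9.9.3 and 9.9.4) also names ITT, but its model keeps the prospective data and the prior data apart and lets the prior in only through the discount function.

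**The concern.** The same term is used in two ways. By the definition in 9.1.3.1, subjects 1-80 belong to ITT. By the wording of 9.9.9, which has to add the feasibility cohort, they may not. Sections 9.9.6 and 9.9.7 do not settle which applies.

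This matters because the result of those 80 subjects was known, and favourable, when this plan was written. The primary analysis reduces their weight when the cohorts disagree. A frequentist ANCOVA on the pooled set has no such reduction. Its p-value could then appear to corroborate the Bayesian result independently while reusing the same 80 subjects at 100%. If the dataset is left open, it can also be chosen after both results are known.

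**Working it through.** **Inputs.** From Table 3 (9.9.4.3): prior RDN mean -8.85 (SE 1.75) and prior control mean -1.80 (SE 1.75), 36 per arm; prospective SD 12. From section 8 and Table 4: 110, 149 and 221 evaluable. Section 9.2 sets two-sided 0.05.

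Assumed prospective arms: 26 × 0.85 ≈ 22 evaluable from subjects 81-106, 11 per arm, and the rest 2:1. This gives RDN/control of 70/40, 96/53 and 144/77.

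**1. Does the planned N include the first 80?** Attrition agrees with the plan: 110/0.85 = 129.4, 149/0.85 = 175.3, 221/0.85 = 260. The discount-prior design was simulated under a normal approximation (40,000 trials, no futility stop, Weibull taken as 1 - exp(-(p/0.25)^3)). Cumulative power was:

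| | 110 | 149 | 221 |
|---|---|---|---|
| Table 4 | 83% | 91% | 96% |
| N counts prospective subjects only | 82% | 91% | 96.5% |
| N includes the 72 prior subjects | 72% | 85% | 94% |

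The planned N is therefore prospective only. The literal ITT set is larger: 80 + 260 = 340 randomised and 72 + 221 = 293 evaluable at the maximum. (The Weibull formula as printed in 9.9.4.1 gives 59%, 74% and 88% and does not reproduce Table 4. That is a separate matter.)

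**2. The known result.** Difference = -8.85 - (-1.80) = -7.05 mmHg; SE = √(1.75² + 1.75²) = 2.47; z = -2.85.

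**3. Raw pooling by arm, no prospective effect, prior fixed as observed.** Let both prospective arms have mean change m, and let N_t = 36 + n_t and N_c = 36 + n_c.
- Expected pooled difference = [36(-8.85) + n_t·m]/N_t - [36(-1.80) + n_c·m]/N_c
- Test SE = 12·√(1/N_t + 1/N_c)
- Conditional SD = 12·√(n_t/N_t² + n_c/N_c²)
- Probability = Φ[(-1.96·SE - expected difference)/SD]

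At 110 with m = -1.8, the arms are 106 and 76, the expected difference is -2.39, SE 1.804, threshold -3.54 and SD 1.376, so Φ(-0.83) = 0.20. With m = -5.3, about the midpoint of the prior arms, the expected difference is -2.86 and the probability 0.31. The result moves with m because allocation changed from 1:1 to 2:1, so a shift in mean between cohorts leaks into the treatment contrast.

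**4. Cohort-stratified pooling.** The prior difference has SE 2.47. The prospective difference has SE = 12·√(1/n_t + 1/n_c) = 2.38, 2.05 and 1.69. Inverse-variance weights give the prior 48%, 41% and 32%. At 110 the expected difference is 0.48 × (-7.05) = -3.39, the pooled SE 1.715, the threshold -3.36 and the conditional SD 1.236, so the probability is 0.51. If SD 12 is used for the prior as well, in place of the 10.5 implied by 1.75 × √36, the probabilities are 32%, 27% and 21%.

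**5. Chance of p<0.05 favouring RDN with no prospective effect**

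| | 110 | 149 | 221 |
|---|---|---|---|
| Raw pooling, m from -1.8 to -5.3 | 20-31% | 16-26% | 13-21% |
| Stratified, Table 3 SEs | 51% | 43% | 34% |
| Prospective subjects only, single look | 2.5% | 2.5% | 2.5% |

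Under stratified pooling the prospective difference needed for significance is about +0.05, -0.4 and -0.7 mmHg, against -4.7, -4.0 and -3.3 mmHg for the prospective subjects alone. Power of a prospective-only test for -5 mmHg is 56%, 68% and 84%.

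**The case against.** Four points can be made in the plan's defence.

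**No rule to pool is stated in 9.9.6 or 9.9.7.** A reader might infer that the plan directs these tests to include the published subjects. It does not say so. Section 9.9.6 is framed around 110 and 149 evaluable subjects, which reproduce Table 4 only as prospective counts, and the added words in 9.9.9 suggest that ITT elsewhere may exclude the cohort. This stands. The defect is a cohort left unfixed under a definition that literally includes it.

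**The primary decision is untouched.** A reader might infer that the ITT definition undermines the primary analysis. It does not: the model separates the two datasets, and the same ITT handling rule can apply to each. Study success rests on the primary Bayesian efficacy and primary safety hypotheses alone (5.1, 9.9). This stands in full.

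**The percentages are not type I error rates of any decision in the plan.** They are conditional on the observed prior result and vary with the pooling model. That is right, and is why a range is given. Conditioning is still the relevant view, because the prior result was already known.

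**Win ratio inclusion is explicit and prespecified.** So nothing is hidden there. But the analysis is called prospective, gives the published subjects full weight and has no prospective-only result planned beside it.

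Restricting every 9.1.3 set to subjects 81 onward might look like the natural remedy. It would conflict with the safety analysis, which uses ITT (9.9.1) and lists the first 106 subjects as a source (Table 2).

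**Conclusion.** The concern holds as a failure to fix the cohort in 9.9.6 and 9.9.7, and as explicit full-weight inclusion in 9.9.9. Under the literal reading, with no effect in the prospective subjects and the prior result as observed, a pooled test of 24-hour SBP would favour RDN at p<0.05 with probability about 20-51% at 110 evaluable, 16-43% at 149 and 13-34% at 221. Even the lowest value, 12.5% before rounding, is five times 2.5%.

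These figures assume SD 12 in the prospective subjects, 22 evaluable from subjects 81-106, no covariate adjustment and a single look. They concern a mean difference in 24-hour SBP. No figure was derived for the win ratio or for the office and diastolic endpoints, for which the SAP gives no prior results. The primary Bayesian conclusion does not depend on this point, so it should be corrected but does not threaten the main result.

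**What to change.** Leave the 9.1.3 definitions and the safety analyses as they are. Then:
- In 9.9.6, in the 6-month between-group tests of 9.9.7 and in 9.9.9, state that the analysis is run on the prospective cohort, subjects 81 onward.
- Show the full-cohort result beside it, labelled as including already published subjects.
- Put a cohort term in any pooled ANCOVA, because allocation changed from 1:1 to 2:1. This removes the leakage from a shift in mean between cohorts. It does not discount the prior subjects, so the label is still needed.

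The cost is a few sentences of SAP text, one extra set of tables, and wider intervals for the prospective-only results. At 221 evaluable the SE of the difference is 1.69 mmHg, against 1.44 (raw) or 1.40 (stratified) when pooled.
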